7.3 Evaluations During and After Treatment

Treatment Day 7, 14, 21, 28 and 42 Assessments.

- Alcohol consumption on Day 28 and 42
- Urinary ethyl glucuronide on Day 28 and 42
- Concomitant medication
- **Dietary calorie and protein consumption*

- *Complete physical examination including WHO performance (and weight on day of discharge)
- *Vital signs (Temperature, systolic and diastolic blood pressure (BP), pulse rate)
- *Laboratory tests: haematology, clinical chemistry (including electrolytes, creatinine, eGFR, LFTs), CRP and prothrombin time
- *Disease scores: mDF, MELD, GAHS
- *Lille score at Day 7
- *Evidence of GI bleed or sepsis in previous 7 days
- *Acute kidney injury
- *Infection/ sepsis/ SIRS screening including
 - Chest X-ray (CXR)
 - Blood cultures (in case of fever)
 - Hepatic encephalopathy
 - Ascitic tap (in case required)
 - MSU
 - Urine culture (in case required)
- EDTA sample for host & bacterial DNA (16S)⁺
- Heparinised sample for PBMC (Monocyte oxidative burst + Monocyte phenotype)[#]
- Serum CK18-M30/M65
- Liver Biopsy at Day 28 (incl. HVPG measurement during trans-jugular biopsy)
- Gene expression tissue sample at Day 28
- Fibroscan at Day 28
- PK/PD
- Exploratory/inflammatory BM serum
- Administration of study drug for patients presenting with AST > 2 x ULN at Day 28
- Duration of hospital stay on day of discharge
- Adverse events
- Stool and saliva sample[#]

[#] PBMC sample not required at on day 21 and 42 or at discharge.

⁺ 16S DNA sample not required on day 42 or at discharge.

[#] Stool and saliva collected at (baseline and) day 14, 28 and 90.

See Schedule of Assessments and Footnote Table for timeframe allowances and full notes relating to sample collection.

7.4 Day 90

- *Alcohol consumption
- Urinary ethyl glucuronide
- Pregnancy test[^] (urinary)
- Concomitant medication
- Dietary calorie and protein consumption
- *Complete physical examination including weight, WHO performance status
- *Vital signs (Temperature, systolic and diastolic blood pressure (BP), pulse rate)

- *Laboratory tests: haematology, clinical chemistry (including electrolytes, creatinine, eGFR, LFTs), CRP and prothrombin time
- Disease scores: mDF, MELD, GAHS
- *Evidence of GI bleed or sepsis in previous 7 days
- *Acute kidney injury
- *Infection/ sepsis/ SIRS screening including
 - Chest X-ray (CXR)
 - Blood cultures (in case of fever)
 - Hepatic encephalopathy
 - Ascitic tap (in case required)
 - MSU
 - Urine culture (in case required)
- EDTA sample for host & bacterial DNA
- Heparinised sample for PBMC (Monocyte oxidative burst + Monocyte phenotype)
- Serum CK18-M30/M65
- Fibroscan
- PK/PD
- Exploratory/inflammatory BM serum
- Adverse events
- Stool and saliva sample

^ Not required in post-menopausal females.

See Schedule of Assessments and Footnote Table for timeframe allowances and full notes relating to sample collection.

7.5 Schedule of Assessments

Table 1 lists all of the assessments and indicates with an ‘x’ at which visits the assessments are performed. Patients should be seen for all visits on the designated day, or as close to it as possible – the visit window/tolerance for each visit is given below the table. At a minimum, patients will be contacted for safety evaluations during the 90 days following randomisation to the study. At this final visit the adverse event and concomitant medications should be reconciled on the CRF. Documentation of attempts to contact the patient should be recorded in the source documentation.

Table 1: Assessment schedule

| | Screening | Baseline 6, 9, 11 | Day 7 ⁴ | Day 14 ⁴ | Day 21 ⁴ | Day 28 ^{2, 11} | Day 42 ^{1, 4} | On Discharge ¹⁰ | Day 90 ³ | Unscheduled |
|--|----------------|----------------------|--------------------|---------------------|---------------------|-------------------------|------------------------|----------------------------|---------------------|-------------|
| Informed Consent | X | | | | | | | | | |
| Demographic data | X | | | | | | | | | |
| Inclusion/Exclusion criteria | X | X | | | | | | | | |
| HIV test [^] | X | | | | | | | | | |
| Pregnancy test ⁺ | X ⁵ | | | | | | | | X | |
| Hepatitis B & C serology[^] | X | | | | | | | | | |
| Genetic sequencing (PNPLA3) | X | | | | | | | | | |
| Urinary ethyl glucuronide | X | X | | | | X | X | | X | |
| Alcohol consumption | X | | | | | X | X | | X | |
| Duration since admission to hospital | | | X | | | | | | X | |
| Medical history | X | | | | | | | | | |
| Prior/Concomitant medications | X | X | X | X | X | X | X | X | X | |
| Vital signs | X | X | X | X | X | X | X | X | X | X |
| Physical exam | X | X | X | X | X | X | X | X | X | |
| Weight | X | | | | | X ¹ | | X | X | |
| Height | X | | | | | | | | | |
| Calorie and protein intake | | X | X | X | X | X | X | X | X | |
| Randomisation | | X | | | | | | | | |
| IMP / placebo administration | | X | | | | X | | | | |
| Prothrombin time | X | X | X | X | X | X | X | X | X | |
| Haematology [%] | X | X | X | X | X | X | X | X | X | X |
| Clinical chemistry [%] | X | X | X | X | X | X | X | X | X | X |
| Serum CK18-M30/M65 sample | | X | X | X | X | X | X | X | X | |
| DF, MELD, GAHS scores | X | X | X | X | X | X | X | X | X | |
| Lille score | | | X | | | | | | | |
| Overt GI Haemorrhage assessment [§] | X | X | X | X | X | X | X | X | X | |
| Acute kidney injury assessment [§] | X | X | X | X | X | X | X | X | X | |
| EDTA sample for DNA (16S) | X | X | X | X | X | X | | | X | |
| PBMC sample [~] | | X | X | X | | X | | | X | |
| Infection/ Sepsis/ SIRS screen | X | X | X | X | X | X | X | X | X | X |
| USS Liver assessment [§] | X | | | | | | | | | |
| Fibroscan measurement [§] | | X | | | | X | | | X | |
| Gene expression sample | | X | | | | X | | | | |
| Liver biopsy (incl. HVPG measurement [*]) [§] | | | X | | | X | | | | |
| Adverse events | | X | X | X | X | X | X | X | X | |
| PK/PD samples in blood and ascites fluid # | | X | X | X | X | X | X | | X | X |
| Biomarker serum | | X | X | X | X | X | X | X | X | |
| Stool & saliva sample | | X | | X | | X | | | X | |

Footnotes to Schedule of Assessments

| | | |
|---------------|--|---|
| ¹ | Day 42 visit | Required for patients who received second dose study drug at Day 28 |
| ² | Day 28 visit | A Day 28 assessment/follow up treatment/biopsy can be performed between Day 25 and Day 35 |
| ³ | Day 90 visit | A Day 90 assessment can be performed 14 days either side of the target date |
| ⁴ | Day 7, 14, 21, 42 visits | For Day 7, 14, 21 and 42 assessments a tolerance of 48 hrs in time window either way is accepted |
| ⁵ | Screening pregnancy test | Needs to be performed as serum test |
| ⁶ | Screening and baseline samples | If baseline visit is performed within 72 hours since screening, then screening samples which repeat at baseline may be accepted on baseline date. |
| ⁷ | Screening and Baseline visit | The maximum time between screening and date baseline is 7 days |
| ⁸ | Baseline liver biopsy acceptance window | The maximum timeframe for a baseline biopsy to be accepted into the trial is 7 days before baseline visit (day of Randomisation and study drug administration). |
| ⁹ | Baseline visit | Allowance of -1 day is accepted to allow for blood results to come through for re-confirmation of eligibility before randomisation and IMP/Placebo administration. Baseline date of visit should always be the date of randomisation and IMP administration. |
| ¹⁰ | Discharge | Patients who are discharged during the follow-up period are not required to attend further weekly visits other than on Day 28 (when the potential second IMP dose and second biopsy is taking place), Day 42 (if second Imp dose was administered) and Day 90, which is the end of study visit. Patients due to be discharged will have the samples collected on discharge, as specified in the schedule of assessments below |
| ¹¹ | Baseline; Day 28 | Sample collection is pre-IMP administration. |
| # | Pharmacokinetic and pharmacodynamics samples - blood and ascitic fluid | In case of ascites, ascites fluid sample needs to be collected only once, at the time when patient is having ascites tapped for clinical purposes. |
| * | TJ liver biopsy | HVPG measurement should be collected in all TJ liver biopsies. |
| ^ | Virology screening | Results within 6 months of screening may be accepted without the need to repeat |
| + | Screening and Day 90 pregnancy tests | Pregnancy test required only for females of reproductive age only |
| ~ | PMBC | PBMC, which are to be sent to a central lab immediately after collection, should not be collected on Friday or Saturday in order to avoid loss of sample due to a weekend staff cover at the central laboratory. When PMBCs are posted out, an email notification must be sent, as per study Lab Manual. |
| % | Haematology & Biochemistry | ± 1 day of screening date |
| \$ | Overt GI haemorrhage assessment, AKI assessment; Fibroscan, USS | From day of admission onwards |

7.6 Assessments

7.6.1 Patient demographics/other baseline characteristics:

Patient demographic and baseline characteristic data to be collected on all patients include: age, gender, ethnicity, source of patient referral, relevant medical history/ current medical condition present before signing informed consent. Where possible diagnoses but not symptoms will be recorded.

Detailed information on the patient's vaccination status (to be recorded as part of prior medication), disease diagnosis and disease related prior medications, surgical and medical procedures that occurred before signing informed consent will also be collected.

Investigators will have the discretion to record abnormal test findings on the medical history CRF whenever in their judgment, the test abnormality occurred prior to the informed consent signature.

7.6.2 Physical exam:

A complete physical examination will include the examination of general appearance, skin, neck (including thyroid), eyes, ears, nose, throat, lungs, heart, abdomen, back, lymph nodes, extremities, vascular and neurological. If indicated based on medical history and/or symptoms, rectal, external genitalia, breast, and pelvic exams will be performed. Weight and height will be measured as per the visit schedule. Physical exam includes WHO performance status.

7.6.3 WHO Performance Status

| | |
|----------|---|
| 0 | Asymptomatic (Fully active, able to carry on all pre-disease activities without restriction) |
| 1 | Symptomatic but completely ambulatory (Restricted in physically strenuous activity but ambulatory and able to carry out work of a light or sedentary nature. For example, light housework, office work) |
| 2 | Symptomatic, <50% in bed during the day (Ambulatory and capable of all self-care but unable to carry out any work activities. Up and about more than 50% of waking hours) |
| 3 | Symptomatic, >50% in a chair or in bed, but not bedbound (Capable of only limited self-care, confined to bed or chair 50% or more of waking hours) |
| 4 | Bedbound (Completely disabled. Cannot carry out any self-care. Totally confined to bed or chair) |
| 5 | Death |

7.6.4 Vital signs

Vital signs will include blood pressure (BP), pulse and body temperature measurements. Systolic and diastolic BP and radial pulse rate will be assessed after the patient has rested in the supine position for at least 3 minutes. Blood pressure should be assessed on the same arm each time measurements are taken. Body temperature should be measured by validated thermometers as commonly used by sites in the respective patient population. The same type of thermometer should be used throughout the study.

7.6.5 Liver biopsy

A liver biopsy is required at baseline visit prior to randomization and on day 28. This may be obtained via a transcutaneous or transjugular route depending on the patient's coagulation status and local expertise. Additionally, where a transjugular liver biopsy is performed, HVPG measurements will also be obtained. The liver biopsy is performed under local anaesthetic and requires the use of X-rays to guide the position of the needle that is inserted to take samples. Two biopsy specimens will be obtained with each liver biopsy; one for histology and one, snap frozen, for gene expression analysis.

All histology samples will be read and scored locally as per usual routine, as well as centrally by [name] at Imperial. Sites should use the widest gauge needle available for biopsy collection. Depending on the size of the needle, up to six passes may be performed; aggregate length of greater than 3cms is necessary and preferably (but not necessarily) obtained in one pass. The sample is to be used for:

- a) Local histology assessment to confirm AH eligibility at baseline and for day 28 comparisons
- b) At the time of liver sample collection, at least 3 and preferably 6 unstained slides (or block) should be prepared for central histology assessment for calculation of primary/secondary outcomes
- c) Snap-frozen sample for gene expression analysis, which is to be prepared from the remaining sample and with at least one or two cores present. The snap-frozen sample should be stored frozen in liquid nitrogen (or at -80) in local sites until batch shipment is arranged at the end of the study.

The prepared unstained slides, together with residual formalin fixed paraffin embedded block should be sent to the central laboratory at Imperial College for central histology assessment. When samples are posted, a notification should be sent to [contact] and [name] – please refer to the laboratory manual for more information.

There should be an H and E (hematoxylin and eosin) and Sirius Red stained sample to enable the local pathologist to confirm the presence of steatohepatitis and 3-6 unstained slides for central lab analysis, which will be stained and digitalized and either returned to the referring sites (if requested by local pathology lab) or stored centrally at Imperial's Tissue Bank. Any remaining material will be used for biomarker analysis.

Biopsies will be assessed initially to confirm that all features of alcoholic hepatitis are present (based on locally histology). The primary endpoint, histological improvement will be measured in the central laboratory and is defined as a reduction in lobular inflammation (regardless of cell type). It will be read by one pathologist, who is blinded with regard to histology slide chronology, type of therapy, and patient clinical status. In addition a sensitivity analysis will be employed by having the histology slide read independently by 2 readers, who are blinded with regard to histology slide chronology, type of therapy, and patient clinical status. Histological improvement will be assessed by direct comparison of pre and post treatment biopsies and recorded as a binary answer, either there is less inflammation present in the biopsy or not. This method of blind biopsy comparison has been used previously (15). Secondary endpoints - AHHS and NAS score- will be measured and compared between active treatment and placebo treatment groups. Further the specimens will be stained and immunohistological findings will be assessed and compared between treatment groups.

7.6.6 Laboratory tests

The **haematology** panel will include: Hemoglobin, white blood cell count with differential including lymphocytes, monocytes, neutrophils and platelet count will be measured. Absolute Neutrophil Count (ANC) will be determined by the laboratory. Prothrombin time will be assessed as well.

The **clinical chemistry** panel will include: alkaline phosphatase, total bilirubin, total cholesterol, LDLC, HDL-C, creatinine, aspartate aminotransferase (AST), alanine aminotransferase (ALT), α -amylase, sodium, potassium, lactate dehydrogenase (LDH), triglycerides, transferrin and CRP; The estimated creatinine clearance will be calculated using the Cockcroft-Gault equation for each creatinine measurement. This will require the information on patient's age, sex, weight, height and serum creatinine levels.

Urine samples will be assessed: Urinalysis (MSU) + assessment for urinary tract infection (UTI); urine white blood cell count with either positive urine gram stain or culture. Urinary ethyl glucuronide will be assessed to control patients' abstinence.

Standard laboratory assessments will be used to determine:

Maddrey Discriminant function (mDF)

$$mDF = 4.6 \times (\text{Prothrombin time (PT}_{\text{PATIENT}} - \text{PT}_{\text{CONTROL}}) + \text{Serum Bilirubin (\mu mol/l}) / 17.1$$

($\text{PT}_{\text{CONTROL}}$ is defined as the mean value at each site; this mean value may be updated on a weekly or monthly basis).

Model for End-Stage Liver Disease (MELD)

$$\text{MELD Score} = 10 * ((0.957 * \ln(\text{Creatinine})) + (0.378 * \ln(\text{Bilirubin})) + (1.12 * \ln(\text{INR}))) + 6.43$$

MELD scores should be UNOS-modified (United Network of Organ Sharing). It is recommended that mdcalc.com (MELD Score - Original, Pre-2016, Model for End-Stage Liver Disease) is used to calculate scores. The Pre-2016 UNOS modification is as follows:

- If the patient has been dialyzed twice within the last 7 days, then the value for serum creatinine used should be 4.0 mg/dL
- Any value less than one is given a value of 1 (i.e. if bilirubin is 0.8 a value of 1.0 is used) to prevent subtraction from any of the three factors, since the natural logarithm of a positive number below 1 (greater than 0 and less than 1) yields a negative value.

NOTE: Pre-2016 MELD does not include serum sodium level. Values used for MELD calculations must be noted in eCRF.

GAHS score

Will be calculated after Forrest et al., 2007

| Score given | 1 | 2 | 3 |
|--------------------------|------|-----------|------|
| Age | <50 | ≥ 50 | - |
| WCC (10 ⁹ /l) | <15 | ≥ 15 | - |
| Urea (mmol/l) | <5 | ≥ 5 | - |
| PT ratio or INR | <1.5 | 1.5–2.0 | >2.0 |
| Bilirubin (μ mol/l) | <125 | 125–250 | >250 |

Lille score

Lille score is calculated as $\text{Exp}(-R)/[1+\text{exp}(-R)]$

where

$R = [3.19 - (0.101 \times \text{age in years})] + (1.47 \times \text{albumin at baseline in g/dL}) + [0.28215 \times (\text{bilirubin at baseline} - \text{bilirubin at Day 7 in mg/dL})] - [0.206 \times (\text{if creatinine} \geq 1.3 \text{ mg/dL at baseline})] - [0.11115 \times \text{bilirubin baseline in mg/dL}] - (0.0096 \times \text{Prothrombin Time in seconds at baseline})$

Change in bilirubin after 7 days

A fall of > 25% will be taken to be a clinically significant fall

Incidence of acute kidney injury

Defined as

- Rise in blood creatinine by 26 micromoles per liter or more within 48 hours
- Rise in blood creatinine over time by 50% or more within the past 7 days
- Urine output less than 0.5ml per kg per hour for more than 6 hours

SIRS

Recommendations of the American College of Chest Physicians/Society of Critical Care Medicine Consensus Conference; Presence of 2 or more criteria out of following:

- **Temperature** < 36 °C or > 38 °C
- **Heart rate** > 90 beats/minute
- **Respiratory rate** > 20 breaths/minute or venous pCO₂ < 32 mmHg
- **Leukocyte count** > 12,000/mm³ or < 4,000/mm³ or band forms > 10%

7.6.7 Infection screening

Diagnosis of infection is based on the criteria outlined by Bajaj and colleagues:

1) spontaneous bacteremia: positive blood cultures without a source of infection; 2) SBP: ascitic fluid polymorphonuclear cells >250/µL; 3) lower respiratory tract infections: new pulmonary infiltrate in the presence of: i) at least one respiratory symptom (cough, sputum production, dyspnea, pleuritic pain) with ii) at least one finding on auscultation (rales or crepitation) or one sign of infection (core body temperature >38°C or less than 36°C, shivering, or leukocyte count >10,000/mm³ or <4,000/mm³) in the absence of antibiotics; 4) *Clostridium difficile* Infection: diarrhea with a positive *C. difficile* assay; 5) bacterial enterocolitis: diarrhea or dysentery with a positive stool culture for *Salmonella*, *Shigella*, *Yersinia*, *Campylobacter*, or pathogenic *E. coli*; 6) soft-tissue/skin Infection: fever with cellulitis; 7) urinary tract infection (UTI): urine white blood cell >15/high-power field with either positive urine gram stain or culture; 8) intra-abdominal infections: diverticulitis, appendicitis, cholangitis, etc.; 9) other infections not covered above; and 10) fungal infections as a separate category. Infection screening will involve chest radiography, urinalysis (mid-stream urine (MSU) culture if urinalysis positive), ascitic tap (if ascites present) and blood cultures if pyrexial.

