2.1 Rationale for IL-1 β inhibition

IL-1 levels are significantly increased in both serum and liver in patients with alcoholic hepatitis as well as in animal models of the disease. Patients with alcoholic hepatitis have serum levels almost 10 times higher than found in healthy controls(7). IL-1 is thought to be responsible for many of the clinical and metabolic characteristics of alcoholic hepatitis including fever, neutrophilia, monocyte activation, anorexia and muscle catabolism (8). In animal models, inhibition of IL-1 signaling considerably attenuates disease severity (9, 10)

IL-1 inhibition using Canakinumab is currently licensed therapy for cryopyrin-associated periodic syndromes, TRAPS, HIDS, systemic juvenile idiopathic arthritis, FMF and gouty arthritis. Canakinumab has demonstrated a favorable risk-benefit profile in patients with these diseases. Previous studies with anti-cytokine therapy in alcoholic hepatitis, targeting the TNF α system, have failed to show a survival benefit due to the increased risk of infection and possibly due to the removal of a regenerative signal provided by TNF α (11, 12). The current protocol will stratify the risk of infection and use prophylactic antibiotics to reduce the risk of sepsis (13).

The current protocol seeks to explore the potential use of Canakinumab in the treatment of AH. AH is a complex disorder in which liver dysfunction results from inflammatory liver injury and cirrhosis and the patient outcome is also determined by susceptibility to infection or the development of acute

kidney injury. In the first instance, it is therefore essential to establish the efficacy of Canakinumab in a proof-of-principle Phase II) study in alcoholic hepatitis. This is best achieved by demonstrating improvement of the hepatic tissue injury histologically.

There is a considerable unmet clinical need in alcoholic hepatitis. At present there is no treatment for patients with this condition which influences mortality rates at 90 days (5). A severe patient population defined by a DF ≥ 32 and MELD ≤ 27 is an ideal group in which to evaluate a new modality of treatment as this group of patients are less susceptible to infection and acute kidney injury could complicate the analysis of a treatment response.

Treatment of alcoholic hepatitis is usually delivered for a 4 week period. Assessment of clinical response can be made after 7 days and is demonstrated by a reduction in the serum bilirubin or the Lille score (14).

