2.4 Rationale for this Study

Currently there is no effective treatment for severe alcoholic hepatitis. Based on our current understanding of the disease pathogenesis IL-1 β is a key mediator of hepatic inflammation responsible for metabolic disturbances, fibrogenesis stellate cell activation and consequently portal hypertension. Canakinumab is a licensed monoclonal antibody inhibitor of IL-1 β and may consequently reverse the adverse effects of the cytokine in patients with this disorder.

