2.5 Rationale for the study population

Patients with severe alcoholic hepatitis defined by a discriminant function ≥ 32 have a mortality rate of around 30% at 90 days after admission. In the recent STOPAH trial we found that patients with a MELD ≤ 27 had 90 day mortality around 22% but had significantly less complications. In particular the incidence of on-treatment infection in patients with a MELD score < 27 was substantially lower in this group of patients. As it is possible that Canakinumab will increase the risk of infection we have chosen to investigate the potential benefit of IL-1 β inhibition in patients with less risk of this complication.

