3.6. Treatment

Patients will be included and randomized and treated before histology result is available. If the histology is negative then patient will be withdrawn.

A single dose of 3 mg/kg Canakinumab or identical placebo will be administered intravenously at baseline (Day 1). Canakinumab will be made up by dilution in 100 ml 5% Dextrose by an unblinded research personnel at each site. The drug or placebo (5% Dextrose alone) will be labelled by the designated unblinded team member.

Patients with moderate to severe ascites should undergo large volume paracentesis prior to administration of Canakinumab.

Patients with AST >2 x ULN on Day 28 will receive a second dose of 3 mg/kg study drug administered i.v. on Day 28:

- Patients who received placebo on baseline will receive placebo.
- Patients who received canakinumab on baseline will receive canakinumab.

The second dose of study drug (or placebo) should not be administered if the patient experienced an incident of infection during the prior 28 days, MELD >27 or in cases where the PI is concerned about the patient's condition deteriorating.

Randomisation will be via the trial InForm database which will enable the unblinded research team to ensure the right dosing and drug preparation in respect of the AST assessment on D28.

4. Patient population

The trial will be conducted in patients with severe alcoholic hepatitis (mDF* ≥ 32 and MELD ≤ 27) with treatment initiated during an index hospital admission with the condition.

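### After dosing, blood cultures and the cellulitis criterion depend on fever, which canakinumab may reduce, so the 90-day infection comparison can be diluted in canakinumab's favour

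*Combined protocol and SAP*

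**What the plan says.** **Trigger for culture.** Section 7.6.7 describes infection screening as chest radiography, urinalysis, "ascitic tap (if ascites present) and blood cultures if pyrexial". The list for Days 7 to 42 in section 7.3 carries the entry "Blood cultures (in case of fever", and section 7.4 has the same condition at Day 90. The sepsis text in 4.4.2 makes pre-randomisation cultures conditional on pyrexia, whereas the screening list in 7.1 sets no such condition.

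**Case definitions (7.6.7).** Criterion 1, spontaneous bacteraemia, requires a positive blood culture. Criterion 6 reads "soft-tissue/skin Infection: fever with cellulitis". In criterion 3, lower respiratory infection, temperature and leukocyte count are alternatives to an auscultation finding.

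**Mechanism.** Section 2.1 states that "IL-1 is thought to be responsible for many of the clinical and metabolic characteristics of alcoholic hepatitis including fever, neutrophilia" are among the features involved. Section 2.4 states that "Canakinumab is a licensed monoclonal antibody inhibitor of IL-1"-β.

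**Why infection is watched.** Section 2.5 explains the choice of a lower-risk population: "As it is possible that Canakinumab will increase the risk of infection". Infection and sepsis over 90 days is a secondary endpoint (3.3). Under section 3.6 the second dose "should not be administered if the patient experienced an incident of infection during the prior 28 days".

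The protocol does not discuss masking of fever. It gives no fever-independent infection definition and plans no sensitivity analysis for this. Section 8.2 leaves the detail of the secondary analyses to a later SAP.

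**The concern.** The sign that prompts the test is one that the active drug may reduce. Blinded staff who apply the rule identically in both arms could still take fewer cultures on canakinumab, so blinding does not remove the problem. The same applies to cellulitis, where fever is part of the definition.

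There are two routes. The one closer to the text is fever caused by the disease. Section 2.1 ties IL-1 to the fever of alcoholic hepatitis, and 4.4.2 notes that culture-negative pyrexia is common in it. Placebo patients may be cultured because of that fever while canakinumab patients lose it. The second route, reduced fever during an infection, is a reasonable inference but is not stated.

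At stake is the main safety comparison. Missed infections on canakinumab would pull the observed ratio down, in the drug's favour. The data monitoring committee (13.3) would see event counts affected in the same way. A missed infection would also be absent from the second-dose decision in 3.6.

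**Working it through.** The plan gives no figure for this point, so there is none to reproduce. The calculation shows how large the effect could be under stated assumptions.

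**Inputs from the protocol:** background infection risk 20-30% (section 2.6); 26 patients per arm (8.1); two-sided 5% tests (8.2).

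**Assumed inputs:** *f*, the share of infections found only if fever is present; *p*₀ and *p*₁, the probability of fever in those infections on placebo and on canakinumab. All other infections are taken as detected equally, and *f* as the same in both arms.

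**Formula.** Detected share = (1 − *f*) + *f* × *p*, so

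observed ratio = true ratio × [1 − *f*(1 − *p*₁)] / [1 − *f*(1 − *p*₀)].

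**Worked case, fever in 70% v 40%:**
- *f* = 20%: (1 − 0.6 × 0.2)/(1 − 0.3 × 0.2) = 0.88/0.94 = 0.94. A true 1.5 reads as 1.40.
- *f* = 30%: (1 − 0.6 × 0.3)/(1 − 0.3 × 0.3) = 0.82/0.91 = 0.90. A true 1.5 reads as 1.35.
- A true 1.5 falls below 1 only if 1.5(1 − 0.6*f*) < 1 − 0.3*f*, that is *f* > 0.5/0.6 = 83%.

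| Fever, placebo v canakinumab | Equal risk, *f* = 20% / 30% | True 1.5, *f* = 20% / 30% | *f* at which 1.5 reverses |
|---|---|---|---|
| 80% v 60% | 0.96 / 0.94 | 1.44 / 1.40 | none |
| 70% v 40% | 0.94 / 0.90 | 1.40 / 1.35 | above 83% |
| 60% v 30% | 0.93 / 0.90 | 1.40 / 1.35 | above 77% |

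**Wider check.** Suppose instead that placebo detection is complete and the drug makes a share *s* of the fever-dependent infections afebrile, so that observed ratio = true ratio × (1 − *f* × *s*). Over *f* = 10-50% and *s* = 25-75%, equal risk reads as 0.975 down to 0.625, and a true 1.5 as 1.46 down to 0.94. Of the combinations tried (*f* = 10, 25, 50%; *s* = 25, 50, 75%), only *f* = 50% with *s* = 75% takes a true 1.5 below 1; *f* = *s* = 50% gives 1.125.

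**In counts.** At 20-30% risk, 26 patients give 26 × 0.2 = 5.2 to 26 × 0.3 = 7.8 infections. With *f* = 20-30%, about 5.2 × 0.2 = 1.0 to 7.8 × 0.3 = 2.3 of these depend on fever. Under 70% v 40% and equal risk, the arms would differ spuriously by 0.3 times that, about 0.3 to 0.7 of an infection.

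**Power.** With 26 per arm, power to detect a true doubling is about 35% (20% v 40%) to 59% (30% v 60%) with full detection. At *f* = 25%, *s* = 50% it is about 22% to 37%; at *f* = *s* = 50%, about 13% to 20%.

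**The case against.** **Much of the screen does not depend on fever.** Chest X-ray, urine tests, ascitic tap and stool-based criteria are unaffected, so SBP, UTI and *C. difficile* are found equally. Most chest infections are too, because an auscultation finding suffices in criterion 3. This stands, and it is why the effect is dilution.

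**Other routes catch afebrile infection.** Criterion 9 covers other infections. Section 4.4.2 records clinical suspicion as sepsis. Section 9.2 requires adverse events to be sought at each contact, and infection is not on the exempt list in Appendix 2. Nothing forbids an off-schedule culture. 16S DNA is taken whatever the temperature. These routes help, but incompletely. Criterion 9 is for infections not already listed, and cellulitis is listed. The clinical-suspicion wording sits in the eligibility text and is not carried into 7.6.7. Adverse event records are not the endpoint definition. 16S DNA is exploratory (3.4), is outside the definition, and is not taken at Day 42 or discharge.

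**The mechanism is not established.** Section 2.1 says only that IL-1 is thought to cause fever, and the drug blocks IL-1β, so suppression may be partial. This stands: the design can bias the comparison, but nothing shows that it will.

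**The trial cannot settle infection risk anyway.** Power is low even with full detection. That is true, but a small trial is read on its counts and ratio, and these should not depend on treatment through the way cases are found.

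**Conclusion.** The point holds as a plausible ascertainment bias, limited to bacteraemia and cellulitis, on a secondary safety endpoint. It can favour canakinumab despite blinding. With 20-30% of infections fever-dependent and fever in 70% v 40% of them, equal risk reads as about 0.94-0.90 and a true 1.5 as about 1.40-1.35. All of these fever figures are assumptions. Confidence is moderate: the trigger wording is plain, but the size is unknown.

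A reader might infer that the rule hides a safety signal or makes harm look like benefit. That follows if the 70% v 40% contrast is applied to every infection (1.5 × 0.4/0.7 = 0.86). The documents do not support this, because most of the criteria in 7.6.7 can be met without fever; under this contrast, reversal of a true 1.5 needs more than 83% of infections to be fever-dependent. Nor do they show that canakinumab abolishes fever during infection.

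The baseline culture condition in 7.2 is not part of the problem, since those samples are taken before dosing. The primary endpoint and the sample size are unaffected.

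**What to change.** For endpoint analysis only:

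1. In 7.6.7 and the SAP, pre-specify an infection definition that does not require fever and is applied blind to treatment, either as the endpoint definition or as a sensitivity analysis. It should count cellulitis without fever, and any clinically suspected infection for which therapeutic (not prophylactic) antibiotics are started. This carries the clinical-suspicion wording of 4.4.2 into the post-dose endpoint. Use 16S DNA as supporting data.
2. Tabulate by arm the number of blood cultures taken per patient and the temperature at sampling, beside the infection result, so that a difference in testing is visible.

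Separately, the blood-culture wording in 7.1 (no fever condition) and 4.4.2 (only if pyrexial) must be reconciled. The sponsor should also consider whether the post-dose trigger fits the drug's mechanism. No clinical culture rule is proposed here.

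**Cost.** A short wording change and one table. Section 8.2 says the SAP is still to be drafted. The infection count becomes slightly broader and less specific. No visits or procedures are added. A bacteraemia that is neither cultured nor clinically suspected will still be missed, and the report should say so.
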